| PK parameters will be calculated using a non-compartmental method from the PK samples collected on Dose 1 and will include but will not be limited to maximum serum concentration (C_{max}), total exposure (AUC), elimination half-life ($t_{1/2}$), clearance (Cl), time to reach maximum concentration (T_{max}) and volume of distribution (V_d). To assess the attainment of steady state, trough (C_{min}) concentrations and peak concentrations (end of infusion) of each dose would be obtained directly from analytical data. |
| Pharmacometric methods may also be applied to further investigate OBI-888 exposure (e.g., accumulation of OBI-888, presence of dose- or time-dependent OBI-888 PK behavior, verification of influential factors on OBI-888 PK). |
| Preliminary Clinical Activity Profile: |
| Tumor response will be evaluated by the Investigator using RECIST version 1.1. Tumor status assessment will be performed pretreatment (up to 28 days prior to dosing). During the study tumor response will be assessed after every second cycle (every 8 weeks) for the first 6 months, then every 12 weeks thereafter. |

| Study Endpoints: | Primary endpoints: |
|---|--|
| | DLTs with OBI-888 AEs/SAEs and laboratory abnormalities as graded by NCI CTCAE |
| | version 4.03 |
| | Secondary endpoints: |
| | Percentage of patients with ORR, CBR, DOR and PFS according to Response Evaluation Criteria in Solid Tumors Version 1.1 (RECIST 1.1) |
| | Percentage of patients with anti-OBI-888 antibodies (ADAs) in blood |
| | • PK and PD parameters of OBI-888 |
| | Exploratory endpoints: |
| | Globo H and related glycan expression in tumor tissue by IHCADCC and CDC |
| | • Identify potential predictive markers by IHC or molecular analysis |
| | Tumor infiltrating Lymphocytes (TILs), including natural killer (NK) cells, and programmed death – ligand 1 (PD-L1) expression in tumor tissue samples by IHC |
| | • Killer cell immunoglobulin-like receptor (KIR), human leukocyte antigen (HLA), and Fc receptor gamma genotype |
| | Glycan analysis of OBI-888 |
| Statistical Methods and Planned Analyses: | Analyses will be conducted by dose level in the dose escalation phase and by cohort in the expansion phase. Descriptive summaries for categorical variables will include counts and percentages. Descriptive summaries for continuous variables will include means, medians, standard deviations, minimum and maximum values. Descriptive summaries of time to event |

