6.3 Discussion of Study Design

This study will be undertaken in patients with advanced cancer that has progressed on prior therapy. In this setting, patients will be seeking to alleviate symptoms of their fatal disease and prolong life through exposure to a novel agent.

Patient safety, and a favorable risk/benefit balance, will be carefully monitored throughout and after treatment. Additionally, attention will be taken to enrolling only patients who are felt to be in sufficient condition to undertake this clinical trial, as defined by adequate performance status, suitable baseline organ function, and the Investigator's determination that there are no significant comorbid conditions which present undue risk. Nevertheless, unexpected toxicity of the investigational drug may occur, and all patients will have informed consent prior to treatment.

In terms of the study design, escalating cohorts for 5, 10, and 20 mg/kg will be assessed using a 3+3 design to identify the MTD and RP2D. Once the MTD and RP2D are established and PK/PD data are carefully evaluated, a cohort expansion will be initiated. The cohort expansion will allow for additional safety data, characterize the PK/PD profile of OBI-888, and evaluate the preliminary clinical activity profile of OBI-888 administered as monotherapy in patients with advanced or metastatic solid tumors.

7 Selection and Withdrawal of Patients

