7.1 Inclusion and Exclusion Criteria

7.1.1 Inclusion Criteria

Patients must meet all of the following criteria in order to be included in the study:

- 1. Male or female patients, 18 years of age or older at the time of consent.
- 2. Provide written informed consent prior to performing any study-related procedure.
- 3. Histologically or cytologically confirmed patients with advanced or metastatic solid tumors will be enrolled, for both Dose Escalation and Expansion.
- 4. Patients must have been treated with established standard-of-care therapy, or physicians have determined that such established therapy is not sufficiently efficacious, or patients have declined to receive standard-of-care therapy.
- 5. Measurable disease (i.e., at least one measurable lesion per RECIST, version 1.1) (Eisenhauer, et al., 2009).
- 6. Eastern Cooperative Oncology Group (ECOG) performance status of 0 or 1 (Oken, et al., 1982).

- 7. Adequate organ function defined as:
 - a. Hepatic:
 - Serum alanine aminotransferase (ALT) ≤3 × upper limit of normal (ULN), ≤5 × ULN in the presence of liver metastases
 - Serum aspartate aminotransferase (AST) $\leq 3 \times ULN$, $\leq 5 \times ULN$ in presence of liver metastases
 - Serum bilirubin $\leq 1.5 \times ULN$ (unless due to Gilbert's syndrome or hemolysis)
 - b. Renal:
 - Creatinine clearance >30 mL/minute using Cockcroft Gault equation
 - c. Hematologic:
 - Absolute neutrophil count $\geq 1000/\mu L$
 - Platelets \geq 75,000/µL
 - Hemoglobin $\geq 8 \text{ g/dL}$
- 8. Patient is willing and able to comply with all protocol-required assessments, visits, and procedures, including a pretreatment tumor biopsy. Archival tumor biopsies (slides or FFPE tissue block) are acceptable at baseline.

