7.1.2 Exclusion Criteria

Patients meeting any of the following criteria are ineligible to participate in this study:

- 1. Less than 3 weeks, from prior cytotoxic chemotherapy or radiation therapy; and less than 5 half-lives or 3 weeks from biological therapies, whichever is shorter, prior to the first dose of OBI-888.
- 2. Has undergone a major surgical procedure (as defined by the Investigator) or significant traumatic injury within 28 days prior to the first dose of OBI-888.
- 3. Presence of an active autoimmune or inflammatory disease requiring systemic treatment

within the past 2 months or a documented history of clinically severe autoimmune disease that requires systemic steroids or other immunosuppressive medications. Local steroid injections, intermittent use of topical, inhaled, ophthalmologic, intra-articular, topical, or intranasal corticosteroids, or systemic corticosteroids at physiologic doses not to exceed 10 mg/day of prednisone or equivalent would not be excluded from the study.

- 4. Presence of primary immunodeficiency or receiving systemic steroids of >10 mg/day prednisone or equivalent or other immunosuppressive agents within 14 days prior to the first dose of OBI-888.
- 5. Has active bacterial, viral, fungal, or mycobacterial infection requiring systemic therapy, including known infection with human immunodeficiency virus (HIV) or active infection with hepatitis B virus or hepatitis C virus. Patients with HIV infection are eligible if CD4+ T-cell counts are ≥350 cells/µL; patients on antiretroviral therapy should be on an established dose for at least 4 weeks and have an HIV viral load less than 400 copies/mL prior to enrollment.
- 6. Patients with a history of solid organ transplant.
- 7. Unresolved toxicities from prior anticancer therapy, defined as having not resolved to Grade 0 or 1 (using NCI CTCAE version 4.03), except for alopecia and laboratory values listed in the inclusion criteria.
- 8. Receipt of any prior therapy targeting Globo H.
- 9. Known hypersensitivity to OBI-888 or its excipients.
- 10. Has known untreated central nervous system metastases. Patients with treated brain metastases are eligible if there is no evidence of progression for at least 4 weeks after central nervous system-directed treatment, as ascertained by clinical examination and brain imaging (magnetic resonance imaging [MRI] or computed tomography [CT]) during the screening period.

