| f. | Post infusion samples at the end of infusion and later (at 1, 3, and 6 hours after the end of the infusion) can be collected in a window of ±15 minutes |
| g. | ADA sample will be collected along with the pre-infusion PK samples according to the above table. For subjects with persistent antibodies at end of study, an |
| | additional ADA sample will be collected at 4 months after the end of study visit. |
| h. | Glycan analysis: Residual PK and ADA samples will be pooled for glycan analysis after PK and ADA data are finalized. |
| i. | Samples should be collected to evaluate tumor-specific biomarkers (eg, CEA for colorectal, gastric, and esophageal cancer; and CA19-9 for pancreatic |
| | cancer). |
| j. | This intensive PK sampling will be collected only from first 3 patients in each cohort. |
| k. | For C1D2 and C1D4, samples can be collected in a window of ±2 hours: |
| | • 24 hours after end of infusion (for infusion at C1D1). |
| | • 72 hours after end of infusion (for infusion at C1D1). |
| 1. | Blood sample will be collected pre-infusion and end-of-infusion. |

- m. For Part B, pre-screening for Globo H tumor sample analysis may occur prior to the screening period for participation in the OBI-888-001 study.
- n. Tumor biopsy samples obtained during the initial screening visit should be used for this assessment.

10 Clinical Activity Profile Assessments

Radiology (CT or MRI scan) evaluations (± 7 days) of tumor response are to be performed during screening within 28 days prior to Cycle 1 Day 1 (first dose of study medication), and thereafter during the study every 8 weeks (Q8wk; ± 1 week) for the first 6 months, then every 12 weeks (Q12wk; ± 1 week). Unscheduled scans can be performed anytime, if needed to confirm disease progression. Radiology assessment for end of study follow-up and early termination should be performed unless the last exam was ≤ 8 weeks prior to permanent discontinuation of study drug. The same assessment method and the same technique should be used on each patient while on study.

Overall tumor response and progression will be evaluated by the Investigator according to RECIST, version 1.1.

11 Pharmacokinetics

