10.2 DEFINITION OF BASELINE, STUDY VISITS, AND VISIT WINDOWS

Baseline for each assessment is defined as the result of the last assessment prior to first dose of study drug. Per protocol, assessments performed at Day 1 should be obtained prior to infusion of the study drug. As only dates (without time) of assessments are recorded, the last assessment with a date prior to or the same as the first dose date will be considered baseline.

The data will be analyzed according to the visits recorded in the eCRF. No additional visit windows will be applied. In listings, any unscheduled visits will be inserted in the appropriate temporal sequence using visit date and time.

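### The baseline scan may precede the last prior anticancer treatment, so any effect of that treatment after the scan would count as OBI-888 activity

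*Protocol*

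**What the plan says.** **Scan window.** Protocol section 10 places the baseline scan "during screening within 28 days prior to Cycle 1 Day 1 (first dose of study medication". The synopsis agrees: "Tumor status assessment will be performed pretreatment (up to 28 days prior to dosing". Table 9-1 gives the screening window as Day -28 to Day -1. Section 10 also attaches a tolerance to scans ("Radiology (CT or MRI scan) evaluations (± 7 days) of tumor response are to be performed") without saying whether it covers the screening scan.

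**Washout.** Exclusion 1 (section 7.1.2) bars patients "Less than 3 weeks, from prior cytotoxic chemotherapy or radiation therapy", and those "less than 5 half-lives or 3 weeks from biological therapies, whichever is shorter", counted back from first dose.

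**Prior-therapy requirement.** Inclusion 4 begins "Patients must have been treated with established standard-of-care therapy, or physicians have determined that such established therapy is not sufficiently efficacious" and also admits patients who declined standard care. It does not require progression on the last therapy. Section 6.3 says "This study will be undertaken in patients with advanced cancer that has progressed on prior therapy", but this describes the population and is not an eligibility criterion.

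**What depends on baseline.** Section 14.1 opens stage 2 of a Part B cohort after at least 1 objective response in 9 patients, and calls the drug worthy of further evaluation after at least 4 in 30. SAP 10.7.2 A analyses CBR. SAP section 11 drops response rate, duration of response, PFS and best overall response.

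**The concern.** The scan window and the washout both run back from first dose, and nothing ties one to the other. If chemotherapy, radiation or a biologic is given after the baseline scan, tumour change caused by it is measured from that scan and attributed to OBI-888. The study has no comparator to reveal this.

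Two outputs are exposed. One is the pair of Part B response rules, where a single response among 9 patients commits a cohort to up to 21 more. The other is CBR, the only tumour-response endpoint that SAP version 2.0 still analyses.

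**Working it through.** **1. Overlap between the two windows**

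- Earliest baseline scan: 28 days before first dose (section 10, synopsis, Table 9-1).
- Latest chemotherapy or radiation: 21 days before first dose (Exclusion 1).
- Overlap: 28 - 21 = 7 days.
- If the 7-day tolerance also applies to the screening scan, which is unclear: 35 - 21 = 14 days.
- Biologics: the limit is min(5 × half-life, 21 days). The documents give no half-lives, so these are assumptions. Half-life 1 day: limit 5 days, overlap 28 - 5 = 23 days. Half-life 2 days: limit 10 days, overlap 18 days. Half-life 4.2 days or more: limit 21 days, overlap 7 days.

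**2. Does any other text close the gap?**

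- Exclusion 12 bars anyone receiving a prohibited medication concurrently, and section 8.6.3 says antineoplastic therapy is not allowed with OBI-888. Neither addresses a treatment that ended 21 days before first dose, which Exclusion 1 accepts.
- Inclusion 4 and section 6.3 do not close it, for the reasons given above. The same holds for the description of refractory or intolerant patients in section 4.5.
- No repeat scan is required after late prior therapy, and recently irradiated lesions are not excluded as targets.

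**3. Reproducing the plan's design**

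Inputs from section 14.1: 9 patients then 30; continue at 1 or more responses, succeed at 4 or more; 5% versus 25%; one-sided alpha 0.05; power 90%.

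- P(pass stage 1) = 1 - (1 - p)^9. At p = 0.05: 1 - 0.95^9 = 0.370.
- P(success) = sum over x from 1 to 9 of P(X = x) × P(Y ≥ 4 - x), with X ~ Bin(9, p) and Y ~ Bin(21, p).
- At p = 0.05: x = 1 gives 0.2985 × 0.0849 = 0.0254; x = 2 gives 0.0629 × 0.2830 = 0.0178; x = 3 gives 0.0077 × 0.6594 = 0.0051; x ≥ 4 gives 0.0006. Total 0.0489.
- At p = 0.25: 0.902.

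The stated alpha and power are met. The design arithmetic is sound, and this point does not change it.

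**4. Illustration of carry-over**

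Assumption: prior therapy adds c percentage points to a true 5% response rate. The documents give no value for c.

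| Added points | Apparent rate | Pass stage 1 | Success (at least 1 of 9, then at least 4 of 30) |
|---|---|---|---|
| 0 | 5% | 0.370 | 0.049 |
| 1 | 6% | 0.427 | 0.083 |
| 2 | 7% | 0.480 | 0.126 |
| 3 | 8% | 0.528 | 0.177 |
| 5 | 10% | 0.613 | 0.294 |

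If carry-over acts only on patients who would not otherwise respond, the apparent rate is 1 - 0.95 × (1 - c). The results are then 0.424 and 0.081 at c = 1%, and 0.603 and 0.278 at c = 5%.

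What c implies: c = share of patients in the overlap × their carry-over response rate. At an assumed 20% carry-over rate, 1 point needs 5% of patients in the overlap, 3 points need 15%, and 5 points need 25%.

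**5. CBR**

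The documents support no estimate of the effect. Each patient wrongly counted moves a cohort's CBR by 1/9 = 11.1 points in a cohort of 9, or 1/30 = 3.3 points in a cohort of 30.

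**The case against.** Much of the opposing case stands, and it limits the point without removing it.

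- **Permitted is not observed.** A reader might infer that shrinkage from earlier treatment is being credited to OBI-888. The documents show only that a compliant sequence allows it. The patient would have to consent, qualify on Globo H in Part B, be scanned, and then receive anticancer therapy during screening. That is a narrow path, and its frequency is unknown.
- **Direction.** A reader might infer that the bias always favours the drug. It does not. In a progressing patient, growth between an early scan and first dose counts against OBI-888. Only the carry-over component is favourable.
- **Persistence.** Response must be confirmed. With scans every 8 weeks, and unscheduled scans described only for confirming progression, shrinkage from a Day -21 treatment would have to show at about Week 8 (8 + 3 = 11 weeks after treatment). It would have to persist to about Week 16 (19 weeks after). This makes carry-over responses less likely but cannot exclude them. The protection is weaker for stable disease, which SAP 10.7.2 A requires to be met at least once 6 weeks or more after first dose; the first scheduled scan could satisfy that.
- **SAP 10.2.** Its rule, "Baseline for each assessment is defined as the result of the last assessment prior to first dose of study drug", might be read as the source of the problem. It is not: overall tumour response is recorded on the eCRF and not derived by program, so the reference scan is set at the site. The rule merely fails to close the gap. RECIST 1.1 is cited, but any timing provision in it cannot be seen in these documents.
- **Importance.** Activity is secondary in a study whose primary objectives are safety and dose, response rate is no longer analysed, and the report is abbreviated.

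**Conclusion.** The point holds as a gap in the ordering of two windows. The protocol allows up to 7 days in which chemotherapy or radiation may follow the baseline scan, and longer for biologics with short half-lives. Nothing in either document requires the scan to come last. Where the sequence occurs, resulting shrinkage or stability would count in CBR and in the Part B rules.

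The size of any bias is unknown. The increase in the chance of passing stage 1 to 43-61%, and of overall success to 8.3-29%, rests entirely on an assumed 1 to 5 points of carry-over. It concerns a response rate that SAP version 2.0 no longer analyses. It shows how sensitive a rule needing 1 response in 9 is to a few misattributed responses; it is not an estimate of the trial's actual error rate.

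**What to change.** **Protocol.** In section 10, the synopsis and Table 9-1 footnote p, state that the baseline scan must be performed after the last dose or fraction of any prior anticancer therapy and within 28 days before C1D1. This closes the 7-day overlap and leaves the washout periods and the 9/30 design unchanged. It helps only patients not yet enrolled.

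**SAP.** In 10.7.2 A, for patients already treated, flag anyone whose baseline scan preceded the last prior anticancer treatment, and show CBR with and without them. Protocol 8.6.2 requires dates of prior treatments to be recorded, and SAP 10.6.3 already lists prior anticancer therapy. If a treatment date is incomplete and could fall after the scan, flag the patient too.

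**Cost.** One sentence, in three places, in the protocol, and one flag and one extra row in the SAP. No scan is added, but some will fall later in screening. The change does not eliminate carry-over: a scan taken the day after the last treatment would comply, yet delayed shrinkage would still be counted.

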11.1 Pharmacokinetic Sampling

Blood samples for pharmacokinetic analysis of OBI-888 levels will be collected at the time points indicated in the Pharmacokinetic Sampling Schedules (Table 9-2 [Part A – Dose Escalation] and Table 9-3 [Part B – Expansion]). The actual date and time of each blood sample collection will be recorded. The timing of PK samples may be altered and/or PK samples may be obtained at additional time points to ensure thorough PK monitoring.

Details of PK blood sample collection, processing, storage, and shipping procedures are provided in a separate laboratory manual.

11.2 Pharmacokinetic Analytical Methodology

The concentration of study drug will be determined from the serum samples using a validated analytical method. Details of the method validation and sample analysis will be included with the final clinical study report.

PK parameters will be calculated using a non-compartmental method from the PK samples collected on Dose 1 and will include C_{max} , total exposure (AUC), $t_{1/2}$, Cl, and V_d. To assess the attainment of steady state, trough (C_{min}) concentrations and peak concentrations (end of infusion) of each dose would be obtained directly from analytical data.

Pharmacometric methods may also be applied to further investigate OBI-888 exposure (e.g., accumulation of OBI-888, presence of dose- or time-dependent OBI-888 PK behavior, verification of influential factors on OBI-888 PK).

12 Safety Assessments

Safety assessments (vital signs, physical examinations, ECG recording, AEs, clinical laboratory results [routine hematology, serum chemistry, coagulation, and urinalysis]) are to be performed at protocol-specified visits, as specified in the Schedule of Assessments, Table 9-1.

12.1 Vital Signs

Vital signs (body temperature, heart rate, systolic and diastolic blood pressure measurements) will be evaluated at the visits indicated in the Schedule of Assessments (Table 9-1). All vital signs will be measured after the patient has been resting in a supine position for at least

5 minutes. Blood pressure measurements are to be taken in the same arm for the duration of the study. Temperature measurement will be obtained as clinically indicated.

Body weight (without shoes) will be recorded whenever vital signs are recorded, and height (without shoes) will be recorded at screening only.

Vital sign measurements will be repeated if clinically significant or machine/equipment errors occur. Out-of-range blood pressure, respiratory rate or heart rate measurements will be repeated at the Investigator's discretion. Any confirmed, clinically significant vital sign measurements must be recorded as AEs.

12.2 Physical Examination

A complete physical examination (head, eyes, ears, nose, throat [HEENT], heart, lungs, abdomen, skin, cervical and axillary lymph nodes, neurological, and musculoskeletal systems) will be performed at screening and early termination. Medical history will be recorded at screening, including smoking history, if applicable.

A limited physical examination to verify continued patient eligibility and to follow up any change in medical history will be performed at the visits indicated in the Schedule of Assessments (Table 9-1). Symptom-driven limited physical examinations will be performed as clinically indicated at any study visit. All changes not present at baseline or described in the past medical history and identified as clinically noteworthy must be recorded as AEs.

Medical history will include previous cancer therapies, cancer history, and past and ongoing concomitant illnesses.

12.3 Electrocardiogram

A 12-lead resting ECG will be obtained at the visits indicated in the Schedule of Assessments (Table 9-1).

At screening, the Investigator will examine the ECG traces for signs of cardiac disease that could exclude the patient from the study. An assessment of normal or abnormal will be recorded and if the ECG is considered abnormal, the abnormality will be documented on the eCRF. ECGs will be repeated if clinically significant abnormalities are observed or artifacts are present.

